3.9 Participant/Subject Withdrawal Criteria

The Main Researcher may withdraw (remove) a participant from some study components at her discretion if participant is non-compliant with required study regimens or procedures.

A participant can voluntarily withdraw from participation in some or all components of a study for which he or she has previously consented if he or she has a valid reason. Withdrawn participants will be replaced only if required sample size is not fulfilled.

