1.3 Other Effects of Areca Nut

Arecoline is the primary alkaloid found in AN and has a numerous effect on the systemic body besides the mouth (Javed F et al., 2010). Arecoline has the **potency to traverse the placental and the blood–brain barrier** besides the oral mucosal tissue. Arecoline is a partial muscarinic agonist that crosses the blood–brain barrier and bind to the gamma aminobutyric acid (GABA) receptors which leads to production of a range of parasympathetic effects such as **accelerated heart rate and increased blood flow** in both the external and common carotid arteries (Asthana et al., 2006). It also has cholinergic effects of **decreasing diastolic blood pressure** (Lin SK et al. 2002). As arecholine can tranverse the placenta barrier; it also is associated with **neonatal withdrawal syndrome and placental damage** (Lo'pez-Vilchez MA et al., 2006).

Giri S et al. (2006) claimed the habitual users of BQ are associated with **dependency syndrome (DS)**. Arecoline is recognized as the **4th most consumed psychoactive substance** in the world; after nicotine, ethanol and caffeine (Giri et al. 2006; Chou et al. 2008; Volgin et al. 2019). Patient with DS usually experiences **increased concentration, mild euphoria, warmth, a sense of well being, relaxation, postprandial satisfaction and a withdrawal**

syndrome associated with insomnia, mood swings, irritability and anxiety, the severity of which can be compared with that of amphetamine use. It also **increases the alertness** of the users, have **anti-migraine properties** and **enhanced capability to work**. In Taiwan, AN serve as an **energizing stimulant** for young industrial workers who needed to endure long hours of repetitive work. Besides that, the betel stalls also **provided a social gathering ground and a sense of community** for the industrial workers that had just migrated to the city (Tham J et al., 2017).

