3.8 Selection criteria

The **inclusion criteria** for this study is as follows:

- ✚ A self-reported BQ chewer who has been chewing BQ for the past 6 months with atleast 2-3 chewing episode per week. The ingredient of BQ must include AN without or without smokeless tobacco.
- ✚ Other optional ingredients such as slaked lime and betel leaf are allowed.
- ✚ Age of participant must be 18 year old or above
- ✚ Participants must be residing in study location (Kota Belud, Sabah)
- ✚ Ability to comprehend, converse and read in Bahasa Melayu and their local language (Bajau)
- ✚ Participants who are able to provide written consent and agree to comply with all protocol-specified procedures such as providing saliva samples, participating in five 1-2 hours sessions of intervention over 22 days and agree to attend follow-up sessions on first and third month

The **exclusion criteria** for this study are as below:

- ✚ Non-Malaysian citizen
- ✚ Participants who are not willing to quit the BQ chewing habit at the time of the study
- ✚ Women who are pregnant or nursing at the time of study
- ✚ Individuals with psychiatric illness or special social situations that would limit their compliance with study requirements

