3.17 Participant Information Sheet and Informed Consent

Participant information sheet (PIS) and informed consent (IF) will be a prerequisite before participants admitted into the study on the screening day. After going through the PIS, participants who refused to provide consent will not be admitted into the study. Nevertheless, the benefits of this study will be emphasized to them.

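### Section 3.9 calls withdrawal voluntary but makes it depend on an undefined valid reason

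*Protocol*

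**What the plan says.** Section 3.9 deals with leaving the study in three sentences.

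- The researcher may remove a participant from some components "at her discretion if participant is non-compliant with required study regimens or procedures".
- The participant's own right begins "A participant can voluntarily withdraw from participation in some or all components of a study" and continues directly "for which he or she has previously consented if he or she has a valid reason".
- On replacement: "Withdrawn participants will be replaced only if required sample size is not fulfilled".

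Two other sections set out what the participant takes on. Section 3.8 admits "Participants who are able to provide written consent and agree to comply with all protocol-specified procedures". Section 3.17 covers consent at the point of entry: "participants who refused to provide consent will not be admitted into the study".

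**The concern.** A right to withdraw that holds only when the reason is acceptable is not voluntary in the ordinary sense. The sentence grants the right in its first half and restricts it in its second. Staff who follow it cannot tell what to do with a participant who gives no reason, or who says only that they have changed their mind.

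The question could arise in practice. Section 1.3, in its background review, describes dependent users as having a withdrawal "syndrome associated with insomnia, mood swings, irritability and anxiety, the severity of which can be compared with that of amphetamine use". Section 3.10.3.2 plans for withdrawal symptoms to be discussed on the quit day. Nothing says whether discomfort of that kind, or plain unwillingness to go on, meets the condition.

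What is at stake is a participant-protection rule that is wrong as written. There is a smaller point about data. Section 3.9 allows withdrawal from only some components, but it does not say that someone who does so will be asked to continue with the questionnaires, and those supply the primary outcome.

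**Working it through.** No arithmetic applies. The plan gives no figure that depends on this clause, and the sample size in Section 3.4 (38 per arm, 76 in total, raised by 16 to 92) does not use it. The check is to read the clause against every other place that deals with consent, compliance or leaving.

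1. **Section 3.9, within itself.** The participant's sentence has two parts: withdrawal is voluntary, and it requires a valid reason. Both hold together only if every reason, including none, counts as valid. The condition would then do no work. If the condition does any work, some withdrawals fall outside the right. Either way the sentence needs changing.

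2. **Section 3.9, definition and procedure.** There is no list or description of valid reasons. No one is named to judge them. No step is given for a reason that is not accepted.

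3. **Section 3.8.** Entry requires agreement to comply with the procedures, including to "agree to comply with all protocol-specified procedures such as providing saliva samples, participating in five 1-2 hours sessions of intervention over 22 days". This states a commitment and gives no way out of it.

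4. **Section 3.17.** It covers people who decline before entry and is silent on those who consent and later wish to stop.

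5. **Section 2.12.** It says that participants who relapse will be supported and brought back into the programme. That concerns a return to chewing, not a wish to leave the study.

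6. **Section 3.10.3.2.** The control and intervention procedures refer to an information sheet and a consent form (Appendices A and B). The Day 15 session foresees possible withdrawal symptoms and answers them with coping strategies. It does not connect them to Section 3.9.

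7. **Section 3.10.1.1 and Appendix M.** The follow-up questionnaire records the number of sessions attended and the reasons for absence. People who miss sessions are therefore already expected at follow-up. What is missing is an explicit request to those who formally stop sessions or sampling.

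Items 3 to 7 contain nothing that overrides the condition in Section 3.9 or grants an unconditional right to leave.

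**The case against.** The strongest reply is that this is loose drafting with no shown effect. Section 3.9 has no refusal step. Staff are told to be supportive and non-judgmental, and participants who relapse are to be encouraged. Faculty ethics approval had already been given (Section 3.16). The information sheet and consent form may well promise withdrawal at any time. Section 3.9 already allows partial withdrawal.

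Much of this stands, and it limits the point. A reader might infer any of the following, and the documents support none of them:

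- **Withdrawal will be refused, for example to someone with withdrawal symptoms.** The protocol does not say so. Because valid is undefined, symptoms might well qualify. The severe syndrome in Section 1.3 is background literature; the session text speaks only of potential symptoms.
- **The Main Researcher decides what is valid.** Section 3.9 gives her discretion to remove participants. It names no one to judge a participant's reason.
- **The clause will increase loss to follow-up, mainly in the intervention arm.** No figure or statement in the protocol supports this. Control participants also have a baseline interview, a booklet explanation, saliva collection and follow-up visits. The restriction in Section 3.15.2 to participants who attended all sessions would exclude those who stop sessions whatever Section 3.9 says. That is a separate matter.

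The reply does not remove the contradiction. Good conduct by staff does not change the written rule. If the consent form gives an unconditional right, Section 3.9 conflicts with it; if it does not, the right is stated nowhere. The edit is needed in both cases.

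**Conclusion.** The point holds as a fault of wording in a participant-protection rule. Section 3.9 calls withdrawal voluntary and then makes it conditional on an undefined reason, with no one named to judge it and no other available section supplying the missing right. On a literal reading, a participant who just wants to stop is not covered.

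The clause applies to every participant in both arms, 92 as planned. It has no numerical effect on sample size, significance level or power, and no effect on attrition can be derived from the protocol. The conclusion about the text rests on Section 3.9 and needs no further assumption. How the rule would operate is unknown, because it depends on consent documents not available here. It should be corrected before enrolment.

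**What to change.** - In Section 3.9, delete the condition that a valid reason is needed. State instead that a participant may withdraw from some or all components at any time without giving a reason, and that a reason is recorded only if the participant offers one.
- Check the information sheet and consent form and make all three texts agree.
- Add that anyone who stops sessions or saliva sampling will be asked, with freedom to decline, whether they will still answer the Day 22, 1-month and Month 3 questionnaires. The existing partial-withdrawal wording allows this; the addition makes it explicit.

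The cost is a sentence or two in Section 3.9 and a check of the consent documents. No extra visits or staff are needed, because the questionnaires are already scheduled. The one small downside is that some withdrawals will have no recorded reason.

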3.0 MATERIALS AND METHOD

3.1 Overview of the Study design

This is a comparative prospective community trial which utilises a cluster randomised controlled trial design involving a Bajau indigenous community in Sabah, Malaysia with a 1:1 allocation ratio. The clusters are Bajau villages that practises BQ chewing habits in Kota Belud district in Sabah. The Bajau villages are the unit of randomisation. There are 39 Bajau villages in Kota Belud, Sabah (Tahir Z et al., 2003).

The clustered randomised controlled trial study design was selected as there was a high tendency of crossover if both intervention and control groups are randomised within the same village. Individuals allocated to a control group may inadvertently receive some aspects of the intervention if they are in proximity to the individuals in intervention group (Hahn S et al (2005). Thus, clustered randomised trial is the best available design for researchers who evaluating intervention that operates at group level, that manipulates the social and physical environment and cannot be delivered to individual participants without any substantial risk of contamination (NIH, 2022).

The eligible villages will be randomised into intervention and control groups based on the required sample size. The intervention group will receive an educational booklet and a structured BQ cessation program which will be cross- culturally adapted first based on a clinical trial (BENIT) by Paulino YC et al. (2020) for a Malaysian high risk population. The control group will only receive an educational booklet.

Baseline information on participant's demographics, BQ chewing behaviours, BQ composition, BQ dependency levels, reasons for chewing, the readiness and self perceived barriers to cease habit will be obtained prior to the commencement of the intervention. The

same participants will be followed-up at 22-day and 3-month after commencement of intervention to assess their of quitting experience and impact of the intervention. Day 22 follow-up was kept in this study as it will enable study results to be compared with similar BQ cessation studies in other parts of the world such as in Pacific Islands (Moss J. et al., 2015 and Paulino YC et al., 2020).

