3.7 Blinding

This study will utilise a single-blinding strategy in which only the researcher implementing the study knows which participant is receiving intervention until the trial is over. A single-blind study makes results of the study less likely to be biased. This means that the results are less likely to be affected by factors that are not related to the intervention being tested.

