3.10.2.3 Training of Intervention Facilitators

A two days training will be conducted by the main researcher. Seven to eight staff who are identified by the Senior District Officer will be involved as questionnaire and worksheet interviewers and verbal translators for this study. Dental officers, dental therapists and dental assistants will be the staff of choice to be the facilitators in this study. They are required to be conversant in Bajau language; especially to support the older section of the participants who are more familiar in their local dialect.

The task of the staff is to explain the questionnaire and worksheets items and to be able to assist participants to complete them as accurately as possible. During the talk sessions, the staffs will act as verbal translators and also assist in the question and answer sessions. The delivery of cessation intervention will mainly be in Malay language delivered by the main researcher. The staff will also assist to collect and verify the responses given by participants in the homework logs such as trigger monitoring logs, trigger management, the non chewing game plan worksheets, social support and thought management worksheets.

During the training, the staff will be introduced to the intervention program; the aims and objectives to achieve, the number and brief explanation about the support sessions and the other method of evaluation at the end of the program. A simulation session will be planned to practically expose the staff to the order and details of this intervention. Staff who are not involved in this study will be recruited to act as a BQ chewers to train the staff who are selected to be the facilitators. The names of all the facilitators will be presented and registered under the National Medical Research Registry (NMRR), Ministry of Health (MOH), Malaysia.

Through the simulation, the main researcher could gain some insight on the possible shortcomings or issues that may arise during implementation. Appropriate remedial action and modification can done before intervention commences. A training manual will be prepared for each staff.

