3.15.2 Data Entry

All data collected will be entered into a Microsoft Excel database, cleaned and then exported to Statistical Package for Social Sciences (SPSS) version 29.0. Descriptive analysis through means and standard deviation will be reported for continuous variable and in the form of percentage for categorical variables and individual items in each domain. A mean and standard deviation also will be calculated for the aggregated domain score. Data of participants that attended all sessions will be analyzed for the cessation rate measurements.

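### Section 3.9 lets the allocation-aware researcher remove non-compliant participants at discretion and have withdrawn participants replaced, with no rule keeping them in follow-up and analysis, which can tilt the cessation comparison towards the intervention

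*Protocol*

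**What the plan says.** On the Main Researcher's powers, section 3.9 of the Protocol says that she "may withdraw (remove) a participant from some study components at her discretion if participant is non-compliant with required study regimens or procedures". Leaving some or all components voluntarily is also possible, "if he or she has a valid reason". On replacement it says: "Withdrawn participants will be replaced only if required sample size is not fulfilled".

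Other sections show who decides and what there is to comply with:

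- **Knowledge of allocation.** Section 3.7 states that "only the researcher implementing the study knows which participant is receiving intervention until the trial is over". Section 3.10.2.3 adds: "The delivery of cessation intervention will mainly be in Malay language delivered by the main researcher".
- **Control regimen.** Section 3.1: "The control group will only receive an educational booklet". Under section 3.10.3.2, controls also return at Day 22, Month 1 and Month 3 for questionnaires and give saliva at Day 22 and Month 3.
- **Intervention regimen.** Five sessions over 22 days (section 3.10.3.2) and seven worksheets (section 3.10.1.3), besides the same follow-up questionnaires and saliva samples.
- **Meaning of compliance.** Section 3.9 gives no definition. Section 3.10.1.1 describes intervention compliance in the follow-up questionnaire as whether the participant has tried to quit since the intervention began, and also assesses it by sessions attended.
- **Analysis.** Section 3.15.2: "Data of participants that attended all sessions will be analyzed for the cessation rate measurements".

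**The concern.** The ground for removal arises after allocation and is related to the outcome. The person applying it knows the arm and delivers the treatment, and no criteria or independent check are stated. The primary outcome (section 3.12.1) is self-reported quitting at Day 22 and Month 3. Someone who never tries to quit is a failure on that outcome and, on one of the section 3.10.1.1 descriptions, also non-compliant. If such people leave follow-up or analysis, and others take their place, the cessation rate among those who remain rises without any treatment effect.

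The rule is neutral in wording but not in reach. Controls can fail only on visits, questionnaires and saliva. Intervention participants can fail on those and on every session and worksheet. Any resulting bias would therefore be expected to favour the intervention.

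**Working it through.** **1. The plan's sample size.** Inputs from section 3.4: 38.64% against 9.09%, alpha 0.05, power 0.80, ratio 1:1. The two-sided two-proportion formula with continuity correction gives 38 per arm, or 76, as stated. The allowance is 38 × 1.2 = 45.6, rounded to 46 per arm, or 92, as stated. The figures reproduce, and the concern does not depend on them.

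**2. When replacement is triggered.** Section 3.4 describes both 76 and 92 as needed. If the required size is 76, replacement starts only after 92 − 76 = 16 losses. If it is 92, any loss that takes the number below 92 triggers it. Section 3.9 does not say which applies.

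**3. Where replacements come from.** Section 3.6 already recruits every eligible villager at screening. A replacement from the same village would be someone not recruited then, entering when the village's arm is known. The alternative is a further matched pair, which section 3.5 allows by selecting pairs until the sample size is met. Section 3.9 gives neither source nor timing.

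**4. Illustration of size.** The removal fractions, the 20% quit rate and the quit behaviour of those removed are assumptions, not document figures. Assume no true effect, the same true quit rate p in both arms, n = 46 per arm, a fraction f removed from the intervention arm only and replaced by compliers, and clustering ignored.

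- If nobody removed would have quit, the apparent intervention rate is p/(1 − f).
- If non-compliers quit at half the compliers' rate, it is p/(1 − 0.5f).
- With d the difference in rates, se0 the pooled and se1 the unpooled standard error, the rejection rate is Φ[(d − 1.96·se0)/se1] + Φ[(−d − 1.96·se0)/se1].

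Worked case, p = 0.0909 and f = 0.2: apparent rate 0.0909/0.8 = 0.1136, d = 0.0227, se0 = 0.0632, se1 = 0.0631. The two terms are about 0.055 and 0.010, together 0.065.

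| True quit rate | Removed | Apparent rate, no quitters removed | Rejection | Apparent rate, half-rate quitters removed | Rejection |
|---|---|---|---|---|---|
| 9.09% | 10% | 10.1% | 5.3% | 9.6% | 5.1% |
| 9.09% | 20% | 11.4% | 6.5% | 10.1% | 5.3% |
| 9.09% | 30% | 13.0% | 9.1% | 10.7% | 5.8% |
| 9.09% | 40% | 15.2% | 14.3% | 11.4% | 6.5% |
| 20% | 20% | 25.0% | 8.8% | 22.2% | 5.8% |
| 20% | 40% | 33.3% | 30.2% | 25.0% | 8.8% |

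The nominal level is 5%. The effect is slight when few are removed and material when many are.

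**The case against.** A reader might infer that only intervention participants can be removed. The text does not say so: the rule covers both arms, and controls can miss visits or saliva. Removals among controls would reduce the net bias. What stands is that the rule bears more heavily on the intervention arm.

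A reader might also infer that removal means leaving the trial. Section 3.9 speaks of some components for the researcher's decision and of some or all for the participant's own, so removal may mean no more than an end to sessions. Other sections point the same way. The follow-up questionnaire records sessions missed and the reasons, section 2.12 would bring relapsed participants back, and session 5 encourages them to try again. What stands is that no sentence keeps removed participants in follow-up or analysis, and that replacing someone suggests the person no longer counts.

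Replacement is conditional. That late entrants would be unusually motivated is conjecture, since section 3.8 already excludes anyone unwilling to quit. Nor does the 20% dropout allowance make replacement pointless, because the condition may apply when losses exceed it.

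Finally, section 3.15.2 already excludes people who miss sessions from the cessation analysis, so while it stands section 3.9 adds little exclusion on that ground. A statistical analysis plan may also define the analysis sets. But neither correcting section 3.15.2 nor a later plan would recover outcomes never collected or undo a replacement.

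**Conclusion.** The concern holds as a defect in a stated conduct rule. An allocation-aware researcher has discretion, without criteria, to remove participants on a ground close to the outcome, and withdrawn participants may be replaced after allocation is known. The likely direction favours the intervention.

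The size cannot be fixed from the protocol. At a 9.09% quit rate the illustrative false-positive rate is about 6.5% with 20% removed and 14.3% with 40%, provided that nobody removed would have quit and no controls are removed. If non-compliers quit at half the compliers' rate, it is 5.3% and 6.5%.

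The documents do not support the stronger reading that the rule acts in one arm only or necessarily breaks the randomised comparison. Nor do they support treating the factors 1/(1 − 0.2) = 1.25 and 1/(1 − 0.4) = 1.67 as expected inflation. Those are worst-case multipliers under assumed removal fractions.

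The valid-reason condition on voluntary withdrawal is a separate point about consent. The consent pages are not available, so how this right was explained to participants cannot be checked.

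**What to change.** Reword section 3.9 to state that:

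- non-compliance may end session attendance only;
- all enrolled participants, except those who withdraw consent for follow-up, are assessed at Day 22 and Month 3 and analysed in their village's allocated arm;
- individuals are not replaced once their village's allocation is known, and any shortfall is met only by adding a further randomised matched pair under section 3.5;
- the required sample size means one named figure, 76 or 92.

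Reconcile section 3.15.2 with this. Separately, delete "if he or she has a valid reason" so that voluntary withdrawal is unconditional.

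The change is one of wording. The observed cessation rate may look less favourable, the evaluable number may fall below 38 per arm, and a further matched pair, if needed, would add fieldwork.
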